1.0 BACKGROUND AND SIGNIFICANCE

Total hip arthroplasty can be associated with significant pain in the immediate postoperative period. In order to mitigate pain and subsequently facilitate patient mobilization and recovery, surgeons can use various methods of analgesia. Two current techniques are a more novel, psoas compartment block, which is gaining popularity for use in total hip arthroplasty with an anterior approach, and a periarticular local anesthetic injection. For a psoas compartment block, anesthetic is introduced directly into the iliopsoas and spreads to the lumbar plexus. For a periarticular local anesthetic infiltration, an anesthetic “cocktail” is injected at multiple spots to the surrounding tissue at the surgical site. To date, it is unclear which of these methods provides the best pain relief during the immediate postoperative recovery period.

It is theorized that the surgeon-delivered psoas compartment block can provide better and more complete pain relief than the “cocktail” injection since it is a consistent technique, and the injection specifically targets nerves that provide the operative area with sensation. Comparatively, the “cocktail” injection can be performed relatively consistently from one case to the next, but there is less knowledge of where the injectate will go and how effectively it will anesthetize the nerves – especially in the subcutaneous tissues.

The proposed study is a prospective, randomized clinical trial comparing patient-reported pain following total hip arthroplasty with a psoas compartment block versus a periarticular local anesthetic infiltration.

2.0 OBJECTIVE

- The primary objective of this study is to examine whether there is a difference in the level of resting pain following total hip arthroplasty with use of a psoas compartment block versus a periarticular local anesthetic infiltration.
- The secondary objective is to examine whether there is a difference in the amount of in-hospital opioid drug use postoperatively

3.0 HYPOTHESIS

- Our hypothesis is that the psoas compartment block will provide better pain relief (as measured by resting pain score) than the periarticular local anesthetic infiltration postoperatively at one or more of six specified post-operative times
- Additionally, we hypothesize less need for in-hospital opioids with a psoas compartment block within 24 and 24 to 48 hours postoperatively

4.0 RESEARCH DESIGN AND METHODOLOGY

We will perform a single-center, prospective, randomized clinical trial with a total of 100 patients. One orthopaedic adult reconstruction surgeon at Beaumont Hospital Royal Oak ([name]) will perform all surgeries. After the patient has consented they will be randomized to one of the following two groups:

- 1.) Psoas compartment block (n=50)
- 2.) Periarticular local anesthetic infiltration (n=50),

The patient will be blinded to the study group.

4.1 Inclusion Criteria

- Patients undergoing unilateral primary total hip arthroplasty by [name] at Beaumont Hospital Royal Oak
- Have a diagnosis of primary osteoarthritis (i.e. degenerative joint disease)
- Surgical approach is anterior

4.2 Exclusion Criteria

- Minors (age less than 18 years)
- Pregnant (surgically sterile, post-menopausal, or negative blood test)
- Previous ipsilateral hip surgery
- Lumbar instrumentation
- Acute trauma
- Rheumatoid arthritis
- Avascular necrosis
- Hip dysplasia
- Known sensitivity, allergy, or contraindication to anesthetics being used in the study
- Narcotic sensitivity
- History of over 6 months of opioid dependency prior to surgery (excluding tramadol)
- Peripheral neuropathy
- Mental/cognitive impairment that would interfere with the patient's self-assessments of function, pain, or quality of life

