4.6 Data Collection

- Primary outcome variable: VAS Pain scores measured at times in Appendix I: Table I
- Secondary outcome variable: Total amount of opioid usage in-hospital (and with 24 hours and 24-48 hours postoperatively)

Demographic and Operative Variables

- Sex
- Age
- Race
- BMI
- ASA score
- Comorbidities, as recorded by anesthesiology
- Date of Surgery
- Time of Surgery
- Laterality (left/right)
- Operative Time (skin incision to skin close, mins)
- Estimated Blood Loss (mL)
- Intraoperative Complications (fracture, bleeding events, etc.)

Outcomes Variables

- Narcotic Use (expressed in oral morphine equivalent units)
- Non-narcotic pain medication usage
- Major Postoperative Complications (DVT, Falls, Infection, etc.) through first postoperative visit
- Units of blood transfused
- Complications related to block/anesthetic
- VAS Resting Pain Scores
- VAS Ambulating Pain Scores
- Time of First Physical Therapy Session
- Length of Hospital Stay (Days)
- Readiness for discharge (days), requiring the following:
 - A pain score of <4 (numeric rating scale) without non-oral narcotics

- Normal eating
- Minimal nausea
- Urination without a catheter
- A dry surgical wound
- No acute medical problems
- The ability to independently transfer and walk 100 feet
- Stable vitals

Pain will be measured on a numeric Likert scale, rating the pain from 0 (none) to 10 (maximal). Scores will be collected at 3 hours postoperatively, in the morning and afternoon on postoperative day one and two and at the post-operative clinic visit. The patient will record their pain on a data collection form that is given to them at each time point. Pain will be recorded for when the patient is at rest and when the patient is ambulating. On postoperative day one and postoperative day two the patient will be asked to fill out the Quality of Recovery Score [Myles] and Opioid-Related Symptom Distress Scale [Apfelbaum, Yadeau] (Appendix I: Table I).

All pain medications will be prescribed per standard of care. Pain medication usage in-hospital will be recorded from Epic. All opioid consumption will be converted to oral morphine equivalents in milligrams. All demographic and operative variables will also be collected for each patient from electronic medical records.

Readiness for discharge will be assessed in both the morning and evening of each postoperative day.

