4.7 Statistical Analyses

A table of descriptive summaries on demographic and operative variables by treatment group will be prepared (means and standard deviations if normally distributed, median and range if not normally distributed, counts and percentages for categorical variables); inference procedures which are consistent with the chosen variable summaries will be used to compare treatment groups.

Before analyzing continuous variables, data sets will be assessed for normality using a Shapiro-Wilk Test and equal variance using the Levene-test. For normal data an independent Student's t-test will be used to compare means, and a Mann-Whitney Rank Sum Test will be used for data that is not normally distributed. The two treatment groups will be compared on categorical variables using the Chi-Square test or a Fisher Exact test for low frequency occurrences.

VAS Pain scores (resting, ambulating) will be compared between groups at each time point using a Mann-Whitney Rank Sum test. A Bonferroni correction will be used to

account for repeated measures and control for a Type I error. A p -value below $.05/6 = .0083$ at each individual postoperative time point will be considered statistically significant. Opioid usage will be compared for total in-hospital as well as broken down by use a 24 hours and use from 24-48 hours using the Mann-Whitney Rank Sum test. A p -value below $.05/3 = .017$ at each individual postoperative time point will be considered statistically significant. Composite scores and subscores of the Quality of Recovery-40 and Opioid-related Symptom Distress Scale, as well as the time to readiness for discharge, will be compared between groups with the t -test or Mann-Whitney Rank Sum test as appropriate.

For all other tests which do not include Bonferroni adjustment, a two-sided p -value < 0.05 will be considered statistically significant. Missing data will be treated as such; there will be no imputation. An exploratory subgroup analysis will also be performed, excluding patients with longer than 3 day stay or patients that required additional surgical intervention. Confidence intervals for the difference in means/medians/odds ratios between the two groups will also be calculated where appropriate. Graduate-trained engineers will analyze data with SPSS statistical software (SPSS Version 20.0, IBM, Inc).

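### Preoperative opioid or tramadol use is allowed at entry but is neither a listed baseline variable nor used in the opioid comparison; recording and stratifying on it is a cheap improvement of uncertain size

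*Combined protocol and SAP*

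**What the plan says.** - **Eligibility (4.2).** The only bar on prior opioid use as such is "History of over 6 months of opioid dependency prior to surgery (excluding tramadol". Tramadol is carved out, and dependency of 6 months or less is not excluded.
- **Variables (4.6).** The baseline list covers sex, age, race, BMI, ASA score, comorbidities and operative items. The nearest entry is "Comorbidities, as recorded by anesthesiology". Preoperative analgesic use is not listed, and the medication data are those of the hospital stay: "Pain medication usage in-hospital will be recorded from Epic".
- **Outcome (4.6).** "Secondary outcome variable: Total amount of opioid usage in-hospital (and with 24 hours and 24-48 hours postoperatively".
- **Randomization (4.4).** 100 patients, 1:1, in blocks. No stratification factor is named.
- **Analysis (4.7).** Opioid use is compared in total, at 24 hours, and as "use from 24-48 hours using the Mann-Whitney Rank Sum test", each at .05/3. No covariate or stratum enters. The only subgroup analysis concerns long stays and additional surgery.
- **Screening (Appendix I, Table I).** Eligibility is reviewed, so opioid history has to be looked at, but nothing carries it into the dataset.

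**The concern.** The protocol treats opioid history as important enough to exclude on, then lets a range of prior use into the trial and does not mention it again. Prior use is a plausible predictor of in-hospital opioid consumption, which is the sole stated secondary objective. If it does predict, leaving it out of the comparison adds between-patient noise to an outcome already tested at a reduced threshold, in a trial whose size (section 4.7.1) rests on literature and feasibility rather than a power calculation. Separately, if one arm happens to include more prior users, a reader of the baseline table could not see it.

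**Working it through.** **Inputs from the documents.** 50 per arm. The threshold per opioid comparison is .05/3 = 0.0167, printed as .017, which agrees after rounding. Section 4.7 states two-sidedness for the unadjusted tests; I assume it for the opioid tests. There is no power figure to reproduce, because no effect size, SD or power is given.

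**Assumptions (none is in the documents).** Prior users make up 10%, 20% or 30% of patients. They consume f = 1.5, 2 or 3 times as much. The true reduction is 35%. Opioid use is log-normal with log SD 0.7, 0.9 or 1.1.

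**Step 1: chance imbalance.** Let the number of prior users in each arm be Binomial(50, p). The SD of the difference in proportions is √(2p(1−p)/50), which is 0.060, 0.080 and 0.092 at p = 10%, 20% and 30%. Ten percentage points is 5 patients. The exact probability of a difference at least that large is 13%, 26% and 33%.

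**Step 2: what such an imbalance does.** On the log scale, users differ from non-users by ln f / SD. At log SD 0.7 this is 0.405/0.7 = 0.58 SD for f = 1.5 and 0.693/0.7 = 0.99 SD for f = 2. A 10-point imbalance shifts the group difference by 0.10 times that, or about 0.06 to 0.10 SD. The assumed treatment effect is −ln(0.65)/0.7 = 0.431/0.7 = 0.62 SD.

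**Step 3: power.** Simulated log use is ln f × (prior user) + ln 0.65 × (psoas block) + Normal(0, SD). Each data set is tested by the planned Mann-Whitney test and by the van Elteren test, which ranks within users and non-users separately and combines the two. Power in %, Mann-Whitney then van Elteren:

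| Log SD | Prior users | f = 1.5 | f = 2 | f = 3 |
|---|---|---|---|---|
| 0.7 | 10% | 70, 72 | 67, 70 | 60, 69 |
| 0.7 | 20% | 68, 69 | 63, 69 | 55, 69 |
| 0.7 | 30% | 68, 70 | 62, 71 | 48, 69 |
| 0.9 | 20% | 45, 45 | 41, 44 | 36, 44 |
| 1.1 | 20% | 30, 30 | 28, 30 | 24, 28 |

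With 3,000 runs the simulation error of a power near 68% is √(0.68 × 0.32/3,000) = 0.9 point, so gains of 1 point are not distinguishable from none. Over 10-30% prior users the gain is about 1-22 points at log SD 0.7 and about 0-10 at log SD 0.9-1.1. If prior use has no effect (f = 1), stratifying loses about 1 point (71% against 70% at log SD 0.7).

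**Step 4: cross-check by another method.** Rank ANCOVA on prior use, with a log-scale effect of 0.65 SD, moves power from 76% to 77% (10% users, 0.5 SD higher), 69% to 76% (20%, 1 SD) and 67% to 76% (30%, 1 SD). The direction is the same and the size similar.

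**Step 5: validity.** With no treatment effect, the rejection rate was 0.013-0.018 for both Mann-Whitney and rank ANCOVA, around the nominal 0.0167. The van Elteren test also held its level within simulation error.

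**The case against.** The strongest reply is that nothing here is an error. Randomization protects the planned comparison, an unadjusted test of a secondary outcome is a common choice, and the plan adjusts for no covariate anywhere. That stands. A reader might infer from the imbalance figures that the planned test is biased or its type I error inflated; step 5 shows that it is not. A 10-point imbalance is 5 patients and moves the group difference by about a tenth of an SD or less for f up to 2.

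Second, the gain rests wholly on assumptions. It is within simulation error at f = 1.5 and shrinks as the log SD rises. The largest gains need threefold use, a high share of prior users and the smallest SD together. The simulation also gives every user the same multiplier, whereas a yes/no field would pool occasional tramadol with nearly 6 months of dependency, so the real gain is probably smaller. This also stands, and it rules out saying flatly that the plan loses power.

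Third, a reader might infer that the information is lost for good if it is not recorded. The documents do not support that. Eligibility review must establish opioid history, section 4.6 already draws on electronic records, and anesthesiology comorbidities may capture some dependency diagnoses. The history could probably be retrieved later. What is missing is a defined field and a prespecified use of it.

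What survives is narrow: a plausible prognostic factor, looked at during screening, is neither reported by arm nor used.

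**Conclusion.** The point holds as a cheap improvement, not as a defect. Sections 4.2, 4.6 and 4.7 together admit prior opioid and tramadol users, do not list that use as a variable, and compare opioid consumption without it. The planned test is valid. It may lose some power: about 1-22 points at log SD 0.7 and about 0-10 at log SD 0.9-1.1, given a 35% reduction, 10-30% prior users and 1.5- to 3-fold use, all of which are assumed. If prior use does not predict consumption, stratifying costs about 1 point. A difference between arms of at least 10 percentage points would occur in about 13-33% of trials and, as the plan stands, would not appear in the baseline table. The calculation concerns the secondary outcome only; it says nothing about the pain scores. Priority: nice to have.

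**What to change.** 1. In section 4.6, add preoperative opioid or tramadol use (yes/no), recorded when eligibility is checked at screening, before randomization.
2. Report it by arm in the baseline table of section 4.7.
3. In section 4.7, prespecify a van Elteren (stratified Mann-Whitney) test for the three opioid outcomes with this item as the stratum, at the existing .05/3 threshold. Keep the unstratified Mann-Whitney test as a sensitivity analysis.

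The cost is one data field, taken from a history already reviewed, and a test outside the basic SPSS menus, so a short script may be needed. Eligibility, treatment and patient contact are unchanged. If the planned test is kept as the main analysis, items 1 and 2 are still worth doing alone.

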4.3 Enrollment and Consent

Patients scheduled to undergo total hip arthroplasty with [name] will be screened preoperatively for eligibility. Patients will be identified by operative schedules. Patients that meet all criteria will be contacted by personnel on the delegation of authority as a

consent provider at least one week in advance of their procedure. After initial contact, if the patient is interested, the research coordinator will offer to email or mail a copy of the consent for the patient to review before consent. The patient will be consented prior to any study procedure or assessments take place. At the time of consent, the patient will have sufficient time to read the consent form and discuss any questions they may have with the consent provider. Patients will be allowed to drop out of the study at any time before their procedure.

4.4 Randomization

The 100 patients in the study will be randomized in a 1:1 ratio to have their procedure performed either with a psoas compartment block or with local anesthetic infiltrate. Randomization assignments will be contained in sequentially numbered, opaque, sealed envelopes, which will be prepared by a statistician in the Research Institute using blocked randomization from The SAS System for Windows version 9.3. After the patient is consented, the consentor will assign the patient to a group following the treatment listed in the envelope and inform the surgeon. Logs will be maintained by consenting personnel to ensure the list is being followed and each patient's group is documented.

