6.0 DATA SAFETY MONITORING AND ADVERSE EVENTS

6.1 Plan for Monitoring and Safety Review

An internal safety monitoring committee will be assembled. Members of group will include a scientific reviewer, two clinicians, and a biostatistician for an independent review of adverse event data provided by the investigator. Members invited to participate in the group are independent of the study. The scientific reviewer is [name]. The clinicians are [name], and attending anesthesiologist, and [name], NP who works at MOI with adult reconstruction patients. The group will meet twice throughout the course of the study to monitor safety, recruitment, subject eligibility, adherence to treatment plan, documentation of dropouts and adverse events. The first meeting will be after 30 patients have completed the study. The second meeting will be after 75 patients

have completed the study. Enrollment will continue while these meetings are being planned and taking place. Members will receive a composite of the collected data including complications and adverse events broken down by study group from the study investigators to review before the meeting. One member will be responsible for taking minutes at the meeting. Reports from all meetings will be presented to the study investigators who will be responsible for reporting the data to the HIC.

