8.0 APPENDIX I

Table I. Schedule of Events

Study Procedures	Screening	Surgery	3 hours postop	POD1 9 AM	POD1 5 PM	POD2 9 AM	POD2 5 PM	3 weeks postop
Visit Windows	-21 to 0 days	N/A	± 1 hours	± 2 hours	± 3 hours	± 2 hours	± 3 hours	± 1 week
Review inclusion and exclusion criteria	X							
Informed consent review and signature	X*							
Study Group Determination (Randomization)	X*							
Intervention (psoas block or periarticular injection)		X						
Collect resting pain score	X ^a		X	X	X	X ^b	X ^b	X
Collect pain with ambulation	X ^a			X ^c	X ^c	X ^{b,c}	X ^{b,c}	X ^c
Quality of Recovery-40 assessment				X		X ^b		
Opioid-related symptom distress scale assessment				X		X ^b		
Assess for adverse events			X	X	X	X	X	X

POD = postoperative day

*Consent will happen before any study procedures or assessment are done and randomization will occur at that time

a. Collected as standard of care in the clinic

b. If patient has been discharged before this time point assessments will not be collected

c. If patient is not ambulating they will have the option of selecting 'N/A'

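### Patients are randomized at consent, up to 21 days before an intervention given during surgery; opening the envelope on the day of surgery would avoid losses in that wait

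*Combined protocol and SAP*

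**What the plan says.** Three places tie randomization to consent. Section 4.0 states "After the patient has consented they will be randomized to one of the following two groups". Section 4.4 adds that "the consentor will assign the patient to a group following the treatment listed in the envelope and inform the surgeon"; it does not say when the surgeon is told. The footnote to Table I in Appendix I reads "Consent will happen before any study procedures or assessment are done and randomization will occur at that time", and the column concerned has a window of -21 to 0 days.

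Section 4.3 puts first contact "at least one week in advance of their procedure". That dates the contact, not the consent, and consent on day 0 is allowed. The same section adds: "Patients will be allowed to drop out of the study at any time before their procedure".

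Sections 4.5.1 and 4.5.2 and the Surgery column of Table I place both interventions within the operation. The Table I row "Review inclusion and exclusion criteria" is marked at Screening only.

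Two provisions touch on losses. Section 4.4 says "Logs will be maintained by consenting personnel to ensure the list is being followed", with each patient's group documented. The Section 6.1 committee meets twice "to monitor safety, recruitment, subject eligibility, adherence to treatment plan, documentation of dropouts and adverse events". Section 4.7 rules out imputation and names no analysis population. No section gives a replacement rule or a dropout allowance.

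**The concern.** The assignment is not needed until the injection is prepared in the operating room, yet it can be made up to three weeks earlier. In that interval a patient can withdraw, have the operation cancelled or moved, or cease to meet the criteria. Each such patient has already used one of the 100 assignments and can have no postoperative pain score. The log and the committee would record these losses but not prevent them.

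Two things are at stake.

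- **Precision.** Fewer patients are analysed than were randomized.
- **Comparability.** Losses bias the comparison only if they differ by arm. Withdrawal by the patient should not differ while the patient stays blinded. The consentor, however, knows the arm, and the single surgeon may know it while the case can still be cancelled or judged ineligible. The documents do not show that this happens.

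With no analysis population named, the handling of patients who were assigned but never treated is also left open.

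**Working it through.** **Timing.** Randomization takes place at consent, within days -21 to 0, and the intervention on day 0. The wait is therefore 0 to 21 days. No section postpones opening the envelope, and none describes preparation specific to one arm that would require earlier knowledge of it.

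**Inputs from the plan.** 100 patients, 1:1 (Sections 4.0 and 4.4); six postoperative time points, each tested at .05/6 (Section 4.7). Check: .05/6 = .0083, as stated. Section 4.7.1 gives no effect size, SD, power or dropout rate, so the 50 per group cannot be reproduced.

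**Assumptions.** Losses of 5% and 10% before surgery, equal in both arms and not replaced; true differences of 0.5 to 0.8 SD.

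**Power per time point.** Normal approximation for two means, with z = 2.638 for two-sided .00833 and n = N/2 per arm:

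Power = Φ(d/√(2/n) − 2.638)

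For d = 0.7:

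- N = 100: √(2/50) = 0.200; Φ(3.500 − 2.638) = 80.6%
- N = 95: √(2/47.5) = 0.2052; Φ(3.411 − 2.638) = 78.0%
- N = 90: √(2/45) = 0.2108; Φ(3.320 − 2.638) = 75.2%

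| True difference | N = 100 | N = 95 | N = 90 |
|---|---|---|---|
| 0.5 SD | 44.5% | 42.0% | 39.5% |
| 0.6 SD | 64.1% | 61.3% | 58.2% |
| 0.7 SD | 80.6% | 78.0% | 75.2% |
| 0.8 SD | 91.3% | 89.6% | 87.6% |

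Before rounding, a 5% loss costs 1.7 to 2.9 points and a 10% loss 3.7 to 5.9.

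**Planned test.** Section 4.7 uses the Mann-Whitney test. With relative efficiency 0.955 (normal data), n is multiplied by 0.955. At 0.7 SD this gives 78.3%, 75.7% and 72.8%: a lower level, and nearly the same loss.

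**Detectable difference at 80% power.** (2.638 + 0.842) × √(2/n) = 0.696, 0.714 and 0.734 SD for N = 100, 95 and 90.

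**At least one of six times** (the wording of the hypothesis in Section 3.0). Assume the same d at every time and a common correlation r, and let W be standard normal:

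Power = 1 − E[Φ((2.638 − d/√(2/n) − √r·W)/√(1 − r))⁶]

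For d = 0.5 and r = 0.5 this gives 81.6%, 79.5% and 77.2%. With r = 0.3 it gives 88.7%, 87.0% and 85.0%; with r = 0.7, 72.9%, 70.6% and 68.0%. These values assume complete scores at all six times. Table I footnote b stops collection on postoperative day 2 after discharge, so they are illustrative only.

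**Not computable.** The share of losses that the change would avoid (it depends on consent dates and on when losses occur), and any bias.

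**The case against.** Randomizing at consent is a legitimate design, and Section 4.4 specifies sequentially numbered, opaque, sealed envelopes prepared by a statistician. The other objections are these.

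- **The wait may be short or nil.** Twenty-one days is an outer bound for the whole screening column. This stands and limits the gain.
- **Few criteria change in three weeks.** Most exclusions in Section 4.2 are stable history or diagnoses; acute trauma and pregnancy are among the few that could change. This also stands, but withdrawal and cancellation remain.
- **Losses could be replaced.** Randomizing 106 patients (100/0.95 = 105.3) or 112 (100/0.90 = 111.1, rounded up to equal arms) would keep 100 treated and recover the power. The plan has no such rule, and Section 4.4 says that 100 are randomized. Replacement would restore numbers but would not shorten the time for which unblinded staff know the arm before surgery.
- **Other missing data may matter more.** If 25% of patients were discharged before the day 2 scores (an assumed figure), n per arm would be 37.5 and power at 0.7 SD at those times would be 65.3% instead of 80.6%. That is far more than the 2.5 points from a 5% loss before surgery. This is fair, and the two problems are separate.
- **A recheck just before opening adds a selection step** in a blocked, single-surgeon trial where earlier assignments are known. Guessing of the next assignment is already possible at consent, but nothing shows that the risk is equal at the two moments. A log makes such exclusions visible; it does not rule them out.
- **Naming the analysis population would settle much of the consequence** without moving randomization. It would fix how losses are handled but would not reduce them.

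**Conclusion.** The concern holds as a low-cost, optional improvement. The timing facts are plain in the text, and the documents give no reason to assign before the day of surgery.

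The likely cost of the present timing is modest: at most about 6 points of power per time point, if as many as 10% are lost before surgery, none are replaced and the true difference is 0.5 to 0.8 SD. These figures measure the cost of losses of the assumed size. They are not a forecast of the gain, since the loss rate and the avoidable share are unknown. No bias is demonstrated.

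**What to change.** 1. Keep consent where it is. On the day of surgery, have existing delegated staff reconfirm and record eligibility. They then open the next sequential envelope as late as drug preparation allows, log the date and time, inform the surgeon, and do not disclose the arm to the patient.
2. Log every consented patient who leaves before opening, with the reason, and use that envelope for the next patient. Include this log in the Section 6.1 committee's review.
3. State in Section 4.7 that everyone whose envelope was opened is analysed as assigned, with patients lacking scores reported by arm.

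**Cost.** Rewording of Sections 4.0 and 4.4; in Table I, moving the randomization mark and its footnote to Surgery and adding an eligibility recheck there; and one sentence in Section 4.7. In practice, envelopes are held at the operating suite, a delegated person must be present to recheck, open and log, and the injection is prepared after opening.

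**Limits.** Losses after opening remain, including day 2 scores not collected after discharge. The surgeon and staff are still unblinded once the arm is known.
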